- To evaluate the effectiveness of typhoid conjugate vaccine (TCV) against blood culture-confirmed typhoid fever stratified by age groups (6 months to <2 years, 2 to 4 years, 5 to 15 years)
- To evaluate the effectiveness of typhoid conjugate vaccine (TCV) against blood culture-confirmed typhoid fever stratified by the period of follow-up (first and second six months) after vaccination
- To determine the immunogenicity of TCV in a subset of participants, stratified by age groups (6 months to <2 years, 2 to 4 years, 5 to 15 years)

f. Methods:

This is a prospective closed cohort, open-label, phase III effectiveness study using a test-negative design of a typhoid conjugate vaccine, ZyVac® TCV (purified Vi capsular polysaccharide of *Salmonella* Typhi conjugated to tetanus toxoid as carrier protein), manufactured by Zydus Lifesciences Limited. The study will be conducted in a closed cohort population among children aged 6 months to 15 years residing in wards 5, 6, 7, 48, 49, 50, 63, 71, and 72 of Dhaka South City Corporation (DSCC). The targeted number of age-eligible children in the study area is ~92,000 among them ~60,000 will be vaccinated. A subset of the first 600 consenting participants will be selected by age strata (6 months to <2 years, 2-4 years, 5-15 years) for enrollment in the immunogenicity study with an additional three follow-up visits. Diary cards will be used to collect adverse events (AEs) following immunization (AEFI) data up to day 7 for a subset of active follow-up of the first 600 vaccinated participants. Participants not in this subset will be encouraged to go to the 'Adverse Event Monitoring Cell' at the Maniknagar field office. Data on serious adverse events (SAEs) will be reported for six months after vaccination. All study updates including AEs and SAEs will be reported to the data safety and monitoring board (DSMB) and sponsor. Passive surveillance for typhoid fever will be carried out in the Maniknagar field office and Mugda Medical College and Hospital in the catchment area among the age-eligible children.

g. Outcome measures/variables:

Primary outcome
Blood culture-confirmed typhoid fever

Secondary outcome
Anti-Vi-IgG antibody concentration
Blood culture-confirmed paratyphoid fever

Description of the Research Project

Hypothesis	to	be	tested:
------------	----	----	---------

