Injection site pain (pain without touching) Or Tenderness (pain when area is touched)	Pain/tenderness causing no or minimal limitation of use of limb	Pain/tenderness limiting use of limb OR Pain/tenderness causing greater than minimal interference with usual social & functional activities	Pain/tenderness causing inability to perform usual social & functional activities	Pain/tenderness causing inability to perform basic self-care function OR Hospitalization (other than emergency room visit) indicated for management of pain/tenderness
Fever	37.7 – 38.6°C	38.7 – 39.3°C	39.4 – 40.5°C	> 40.5°C
Malaise	Symptoms causing no or minimal interference with usual social &	Symptoms causing greater than minimal interference with usual social &	Symptoms causing inability to perform usual social & functional activities	Incapacitating fatigue/ malaise symptoms causing inability to

	functional activities	functional activities		perform basic self- care functions
Myalgia	Muscle pain causing no or minimal interference with usual social & functional activities	Muscle pain causing greater than minimal interference with usual social & functional activities	Muscle pain causing inability to perform usual social & functional activities	Disabling muscle pain causing inability to perform basic self-care functions

All adverse events related to vaccination, as judged by a medically qualified investigator, occurring during the first 7 days post-vaccination that are observed by the study team/investigator or reported by the participant's parent/guardian, will be recorded on the CRF. The information will be collected both passively and actively.

For active surveillance of a subset of 600 participants, information will be actively collected via phone calls or home visits. Parents of participants not in this subset will be encouraged to go to the 'Adverse Event Monitoring Cell' at the Maniknagar field office which will have a medical doctor and also available on-call 24 hours a day for adverse event monitoring throughout the whole vaccination period + 7 days.

The following information will be recorded: description, date of onset and end date, severity, assessment of relatedness to study medication, and action taken. Follow-up information should be provided as necessary.

The severity of events will be assessed on the following scale: 1 = mild, 2 = moderate, 3 = severe, 4 = Potentially life-threatening

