All Serious Adverse Events (SAEs) observed by the Investigators, members of the study team, or reported by the parent/guardian will be recorded on CRFs.

Throughout the study period

Serious Adverse Events (SAEs), as judged by a medically qualified investigator, observed by the investigator, or members of the study team, or reported by the parent/guardian, will be recorded on the CRF.

The following information will be recorded: description, date of onset and end date, severity, assessment of relatedness to study medication, and action taken. Follow-up information should be provided as necessary.

All SAEs will be recorded in the CRFs, for the entire study duration. Participants with SAEs will be followed by a medically qualified investigator either until resolution or the event is considered stable.

Reporting procedures for serious adverse events

The forms developed by the icddr,b institutional review board (IRB) will be used for reporting all SAEs.

All SAEs occurring within the 6 months post-vaccine administration will be reported to the Data Safety Monitoring Board (DSMB), Directorate General of Drug Administration (DGDA), the PI, and the other study investigators within 24 hours of the site study team becoming aware of the event. A more detailed report form will be completed and sent within the shortest period of the initial report, to all parties mentioned above. Additional and further requested information (follow-up or corrections to the original case) will be detailed in subsequent safety report forms. All SAEs must be reported to the study sponsor within 7 days. Summary reports will be submitted to the icddr,b IRB, and DGDA at the end of the study.

All SAEs will be reported to sponsor at below mentioned email ID:

[contact], [contact]

Indication for antipyretics and analgesics

Antipyretics will be used in case of fever (axillary temperature >38°C/100.4°F or feels hot to touch) following vaccination. Analgesics will be used in case of pain, or discomfort after getting vaccinated.

Safety monitoring committee

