A DSMB will also be formed to oversee the safety component of the study. The DSMB members will not be involved in the study in any way. In addition, a physician with relevant study-related or therapeutic expertise will be identified as an independent safety monitor (ISM). The ISM will not be an investigator for this study. Under any circumstances, the identified ISM would be requested to carry out an independent assessment of the child presented with adverse events. The assessment details will be reported to the PI and DSMB.

Pregnancy follow-up

Follow-up on pregnancy outcomes will be conducted for all married girls identified during routine follow-up as either being pregnant at the time of vaccination or becoming pregnant within three months of vaccination. This follow-up will include monthly visits until the end of the pregnancy, with the final contact occurring after delivery or pregnancy outcome. Starting from the eighth month of gestation, additional weekly follow-ups will be conducted via phone calls. We will record pregnancy-related information considering it as a medically important event.

Immunogenicity study

A subset of 600 participants will be enrolled in the immunogenicity sub-study and will have an additional three face-to-face follow-up visits at the field office at one month (D30/+7 days), at 6 months (D180+/-14 days), and at one year (D365+/-30 days) after vaccination. The first 200 participants from each age stratum (6 months to <2 years, 2 to 4 years, 5 to 15 years) who give their consent will be selected and enrolled for the immunogenicity sub-study.

At these additional visits, the following procedures will be performed:

- Confirmation of continued participation in the study
- Collection of blood (3ml for 6 months to 4 years and 5ml for 5 to 15 years)
- Confirmation of contact details and reiteration of instructions to attend the health care facilities in case of fever for ≥2 days and/or temperature ≥38°C at presentation.

The above information will be recorded in the immunogenicity CRF. Parents/guardians of participants enrolled in the immunogenicity study will be given details of the follow-up appointments.

Surveillance for enteric fever

[figure not shown]

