Surveillance for enteric fever will be undertaken at the Maniknagar field office and Mugda Medical College and Hospital for all age-eligible (from 6 months to 15 years) residents recorded in the baseline list. Participants with a subjective history of ≥2 days of fever and/or a temperature of ≥38°C at presentation will be enrolled in the surveillance. A blood sample (3ml) will be collected for microbiological culture. The participants will receive appropriate clinical management. Blood culture-positive patients will be visited at home to confirm their identity, and collect information about their illness and patients will be asked to visit the field office if their condition is not improved. The treatment will be adjusted as necessary, based on laboratory testing.

Study staff will visit households, included in the baseline listing, periodically, to remind them to seek treatment at the Maniknagar field office if their children (both vaccinees and non-vaccinees) develop a fever.

Eligibility criteria for enrollment in the passive surveillance

- Participants information, available in the listing database
- Parent/guardian is willing and competent to provide informed consent. For participants aged 11 to 15 years, informed assent will also be considered
- Participants from the study area who experienced a fever lasting for ≥2 days and/or temperature ≥38°C at presentation [4, 30]
- Participants aged 6 months to 15 years on the first day of the vaccination campaign

Flow diagram

Laboratory procedures

Passive surveillance samples

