SOP and training																						
materials																						
development																						
Training for																						
vaccination and																						
surveillance																						
Listing of																						
interested children																						
for vaccination in																						
the study area																						
Vaccination																						
AEFI recording																						
SAE recording																						
and reporting																						
Diary card review																						
Patient enrollment																						
in the passive																						
surveillance																						
Patient																						
management																						
Sample collection																						
for imunogenicity																						
and passive																						
surveillance																						
Laboratory																						
analysis																						
Data cleaning																						
Development of																						
statistical analysis																						
plan																						
Data analysis																						
Clinical study																						
report (CSR)																						
development																						
Manuscript																						
writing and																						
submission																						
Dissemination of																						
findings in																						
national and																						
	 	1	1	 	 	l	l	l	1									1	1	1		

international											
community											

Sample Size Calculation and Outcome (Primary and Secondary) Variable(s)

Clearly mention your assumptions. List the power and precision desired. Describe the optimal conditions to attain the sample size. Justify the sample size that is deemed sufficient to achieve the specific aims.

A sample size of 515 (103 cases and 412 controls) will be required in this case-control test-negative design study assuming vaccine effectiveness of 80%, vaccine coverage of 65% in the target age-eligible population (6 months to 15 years), 4 controls per case, precision width of \pm 10% (20%) and type 1 error rate of 0.05. Considering the incidence rate for typhoid fever of 230 per 100,000 person-years among the non-vaccinated population aged 6 months to 15 years, the target number of vaccinations is \sim 60,000.

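### SAEs are to be followed for six months, but for 99% of vaccinees the only dedicated reporting channel closes 7 days after the campaign and no later contact is described as asking about them

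*Protocol*

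**What the plan says.** The protocol sets two time spans for SAEs. The Project Summary (Methods) says "Data on serious adverse events (SAEs) will be reported for six months after vaccination", and the section on reporting SAEs repeats six months for notification to the DSMB and the regulator, within 24 hours of the team becoming aware. Under the heading for the whole study period, the protocol adds: "All SAEs will be recorded in the CRFs, for the entire study duration". The events meant are those that the investigator or study team observes or that a parent or guardian reports.

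The population is large: "The targeted number of age-eligible children in the study area is ~92,000 among them ~60,000 will be vaccinated".

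Active adverse event collection (a diary card and a contact at about day 7) covers 600 children, 200 per age stratum. Other parents are encouraged to come to the Adverse Event Monitoring Cell at the Maniknagar field office, which has a doctor and is "available on-call 24 hours a day for adverse event monitoring throughout the whole vaccination period + 7 days". Unsolicited adverse events are to be recorded for 28 days.

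The later contacts are these:
- For all listed households: "Study staff will visit households, included in the baseline listing, periodically, to remind them to seek treatment at the Maniknagar field office" if a child develops fever.
- Surveillance at two facilities, which enrols children with fever.
- For the 600 only, visits at one month, six months and one year. The listed procedures are "Confirmation of continued participation in the study", a blood draw, and contact details with a reminder of the fever instructions.

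**The concern.** A six-month SAE commitment needs some means of finding the events. As written, the dedicated means stops early for nearly all vaccinees, and no later contact is described as asking about hospital admission or death. A child admitted elsewhere without fever, or a death at home, is recorded only if the family thinks to tell the study.

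What is at stake is the interpretation of the SAE count. The DSMB oversees safety, and the Background section says that the study serves a WHO prequalification application. If few SAEs are listed beside 60,000 vaccinees, a reader will tend to see a low rate when part of the follow-up was never observed. The events captured would also lean towards children who come in with fever, because that is the contact the design promotes. Pregnancies within three months of vaccination have the same weakness. They are to be picked up in routine follow-up, but no follow-up contact that asks about pregnancy is described outside the subset, and the listed subset visits do not mention it either. Events missed in the field cannot be recovered at analysis.

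**Working it through.** **Inputs.** About 92,000 eligible children, 65% coverage and about 60,000 vaccinees (Project Summary; Sample Size Calculation). Active subset of 600. Cell open for the vaccination period plus 7 days. Unsolicited event window of 28 days. SAE reporting window of six months, taken as 180 days.

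**1. The plan's own denominator.** 0.65 × 92,000 = 59,800, which agrees with the stated figure of about 60,000.

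**2. Share outside active follow-up.** 60,000 − 600 = 59,400, and 59,400 / 60,000 = 99.0%. With 59,800 as the denominator it is 59,200 / 59,800 = 99.0%.

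**3. Time for which the cell is open.** A child vaccinated *d* days before the last campaign day has the cell for *d* + 7 days.
- Last day (*d* = 0): 7 / 180 = 3.9% of the six-month window, and 7 / 28 = 25% of the unsolicited event window.
- To cover 28 days, *d* must be at least 21. Children vaccinated later than that outlast the cell even for unsolicited events.
- To cover 180 days, *d* must be at least 173.

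The campaign length cannot be read, because the timeline cells were lost. If it is assumed to last *L* days with even uptake, mean coverage is *L*/2 + 7 days. For *L* = 30 this is 22 days (22 / 180 = 12%), and for *L* = 90 it is 52 days (52 / 180 = 29%).

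**4. What remains after the cell closes.**
- Household visits: all listed households; stated purpose is the fever reminder; no SAE question described.
- Facility surveillance: entry requires fever, so non-febrile events, admissions elsewhere and deaths at home do not enter.
- Visits at one month, six months and one year: the 600 only; no SAE question among the listed procedures.
- Spontaneous report or staff observation: open throughout, but nothing prompts it.

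**5. What a zero count could mean (bounding illustration).** With no events among *n* fully ascertained children, the one-sided 95% upper limit is 1 − 0.05^(1/*n*). For *n* = 600 it is 0.50%; for *n* = 60,000 it is 0.005%. At a true rate of 1 in 10,000, the expected counts are 600 × 0.0001 = 0.06 and 60,000 × 0.0001 = 6. Under the present text, the information in a zero count lies at an unknown point in this range. Even the lower end assumes that the 600 are asked about SAEs for the full six months, which their listed procedures do not ensure.

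**The case against.** The strongest reply is that passive SAE collection in everyone, with active follow-up of a subset, is a coherent design. The limit on the cell belongs to the section on the first 7 days. The next heading covers the whole study and keeps SAE recording open. This stands. A reader might infer that SAEs after the cell closes cannot be recorded, and the protocol does not support that. Nor do the six-month and whole-study statements contradict each other, since one governs reporting and the other recording.

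Other parts of the text also help. The study pays for medically necessary inpatient care, which gives families a reason to mention an admission. It is present at one hospital. The withdrawal section mentions access to hospital records, though only for the primary outcome. Staff at household visits belong to the study team and may notice events. These make some capture likely, but none makes it systematic.

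A reader might also infer that the protocol plans a six-month SAE rate over 60,000 that will be biased by a known amount. It does not. Safety is not a listed objective, the planned safety analysis is descriptive, and the share missed cannot be derived. The last-day figure of 7 days is the extreme case.

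Finally, the timeline cells, the flow diagram and the consent pages are not visible, so families may be told elsewhere how to report a serious event. That would make spontaneous reporting better, but it would not turn the described contacts into enquiry.

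**Conclusion.** The point holds as one of incomplete ascertainment. About 59,400 of 60,000 vaccinees (99%) have no described contact with a listed SAE question at any time in the six months. Their dedicated channel can be as short as 7 of about 180 days, which is also shorter than the 28-day unsolicited event window for children vaccinated late in the campaign. Later SAEs remain recordable, but only through spontaneous reports or chance observation, so the count is probably incomplete and weighted towards febrile attenders. A low count therefore cannot be read as reassurance.

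The 99% and the 7 days come directly from the protocol. The 12% to 29% mean coverage rests on an assumed campaign of 30 to 90 days with even uptake. The size of the shortfall in events is unknown. Primary effectiveness is not affected. This should be changed before vaccination starts, because it is fixed by field procedures and not by analysis.

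**What to change.** - Add one fixed question to the one-month, six-month and one-year visits of the 600: any hospital admission, death or pregnancy since vaccination or the last contact, with the date.
- Ask vaccinees' families the same question at the periodic household visits already planned, and schedule one of those visits near six months after vaccination where feasible.
- State how parents report an SAE after the Monitoring Cell closes, and reconcile the cell's closing date with the 28-day and six-month windows.
- State that SAEs outside the subset are otherwise spontaneous reports and must not be presented as a complete rate over about 60,000 vaccinees. Report the number of vaccinees actually asked, and when, beside any SAE count.

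The cost is a short form, slightly longer visits and more SAE reports to process under the 24-hour rule, many of which are likely to be background events. The protocol says only that household visits are periodic, so a visit near six months for every vaccinee is not shown to be planned already and may need extra field time. If it is not feasible, the statement about spontaneous reporting is the minimum.

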- Parent/guardian is willing and competent to provide informed consent (if the participant is 11 to 15 years of age, assent will also be sought)
- Participants aged between 6 months to 15 years (i.e. up to 15 years 364 days) at the time of vaccination
- Apparently healthy (no complaints of febrile illness) on the day of vaccination
- Parent/guardian confirms that their child will be willing and be able to comply with study requirements

Exclusion criteria for vaccination:

The participant will not be enrolled if any of the following criteria apply:

- Has knowingly received a typhoid vaccine in the past
- Known allergy to any vaccine in the past
- Medical or social reasons that will prevent the participant from conforming to the study requirements as judged by a medical professional
- Planning to move away from the catchment area within the next 12 months
- Pregnant at the time of vaccination, as confirmed by a urine test (urine pregnancy test will be done in girls who are married)
- Confirmed or suspected immunosuppressive or immunodeficiency disorder; or subjects on any immunosuppressive or immunostimulant therapy
- Subject participated in another clinical study in the past 3 months

Temporary exclusion criteria for vaccination:

Participants will be temporarily excluded from being vaccinated if, at the point of vaccination, any of the following apply:

- Receipt of any other vaccines in the last 30 days
- Current temperature of at least 38°C or reported fever within 24 hours prior to vaccination
- Use of antipyretics within 4 hours prior to vaccination
- Unmarried girls between the ages of ≥12 to 15 years old whose first day of their last menstrual period (LMP) is more than 28 days ago or who do not know the date they last menstruated upon presentation

If these apply, the participant will be temporarily excluded from vaccination until the temporary exclusion criteria no longer apply. Please note, for children with fever above 38° C this must be a minimum of 48 hours after the fever has resolved. Unmarried girls between the ages of ≥ 12 to 15 years whose first day of their LMP is more than 28 days or who do not know the date they last menstruated upon presentation will be asked to return after starting their next

menstruation for vaccination. A re-assessment will be conducted to ensure these temporary exclusion criteria no longer exist.

Verification of the potentially eligible children

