An informed written consent will be obtained after confirming the participants by checking the database. After proper consenting process, a temperature will be taken and parents will be asked about antipyretic use and timings of previous vaccination to assess temporary exclusion criteria. A brief medical history will be taken and eligibility will be assessed against inclusion and exclusion criteria. Participants with temporary exclusion criteria will be informed and asked to return 48 hours after the fever has resolved or 30 days after the last vaccination was given for repeat assessment and reconsent. Unmarried girls between the ages of ≥12 to 15 years whose first day of their LMP is more than 28 days or who do not know the date they last menstruated upon presentation will be asked to return after starting their next menstruation, for vaccination. A member of the study team will collect/edit demographic information (including age and address) and participant contact details by screening case report form (CRF). After completion of the eligibility checking, a sticker will be allocated for the participant which includes the information of vaccination ID and temperature; these will be used in the vaccine accountability log.

Vaccination

The vaccination team will finally check the identification and then administer the vaccine. After vaccination, information will be recorded in the vaccination CRF. If the participant is included in the immunogenicity study, a blood sample will be taken by a suitably trained staff member before vaccination. After administration of the study vaccine, participants will be asked to wait at least 30 minutes for any immediate hypersensitivity reactions or any other adverse

events (AEs). The female participants of reproductive age should have been advised not to be pregnant within three months after the vaccination.

Investigational Medicinal Product (IMP)

Purified Vi capsular polysaccharide of *Salmonella* typhi conjugated to tetanus toxoid as carrier protein (Typhoid Vi Conjugate Vaccine I.P.). Trade name: ZyVac® TCV, Zydus Lifesciences Limited.

Each 0.5ml vaccine dose contains:

- Purified Vi-capsular polysaccharide of S.typhi 25 μg
- conjugated to tetanus toxoid (carrier protein) 16 to 50 μg
- 2-Phenoxyethanol (as preservative) 2.50 mg
- Isotonic buffer solution q.s.

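### Pregnancy precautions at vaccination apply to girls whatever their marital status, but pregnancy-outcome follow-up is limited to married girls found at an undefined routine follow-up

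*Protocol*

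**What the plan says.** Three parts of the protocol deal with pregnancy around vaccination.

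- **Entry.** Under Exclusion criteria for vaccination, pregnancy excludes, and "urine pregnancy test will be done in girls who are married". The Temporary exclusion criteria add a rule for the others: "Unmarried girls between the ages of ≥12 to 15 years old whose first day of their last menstrual period" was more than 28 days ago, or who do not know the date, are deferred until their next menstruation. Screening and eligibility assessment repeats this rule.
- **Advice.** The Vaccination section says: "The female participants of reproductive age should have been advised not to be pregnant within three months after the vaccination". It sets no marital limit.
- **Outcome follow-up.** The Pregnancy follow-up section says: "Follow-up on pregnancy outcomes will be conducted for all married girls identified during routine follow-up as either being pregnant at the time of vaccination", or as "becoming pregnant within three months of vaccination". These girls are visited monthly until the pregnancy ends, with weekly calls from the eighth month. The section closes by saying that pregnancy-related information is recorded as a medically important event.

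The protocol does not define routine follow-up.

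**The concern.** The group followed for pregnancy outcomes is narrower than the group to which the precautions apply. The menstrual-date rule does not name pregnancy as its reason. Even so, it stands beside the urine test for married girls and is naturally read as its counterpart for unmarried girls. The plan thus allows for pregnancy in unmarried girls at entry and in the advice, and then leaves them out of outcome follow-up.

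The section also promises to cover all married girls in the stated window, but only those found at routine follow-up. If that means the dated study contacts, nearly all vaccinees have none. A report of few or no exposed pregnancies could then reflect who was followed and how they were found. At stake is the completeness of safety data on exposed pregnancies in minors.

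**Working it through.** **1. Who is covered, section by section**

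| Section | Married girls | Unmarried girls |
|---|---|---|
| Exclusion / Temporary exclusion criteria | Urine test | Deferral by menstrual date, 12 to 15 years |
| Vaccination (three-month advice) | Yes, if of reproductive age | Yes, if of reproductive age |
| Pregnancy follow-up (visits to outcome) | Yes | Not included |
| Recording of serious adverse events | Yes | Yes |

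The third row is the only one that turns on marital status to leave a group out.

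**2. Who has a dated individual contact**

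Inputs:
- About 60,000 planned vaccinees (Project Summary, Methods).
- A subset with 200 in each of three age strata (Adverse events follow up; Immunogenicity study).
- Contacts at day 7, D30, D180 and D365, all for that subset (same sections). Withdrawal of participants likewise ties follow-up calls, visits and blood tests to the subset.

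Arithmetic:
- The plan's own figure is reproduced: 3 × 200 = 600.
- Share of vaccinees with dated contacts: 600 / 60,000 = 1.0%.
- Vaccinees without them: 60,000 − 600 = 59,400, or 99%.
- Only the oldest stratum can contain girls of 12 to 15 years: at most 200, and 200 / 60,000 = 0.33%. The true number is smaller, because that stratum also holds boys and children of 5 to 11 years.

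**3. Timing**

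The three months define when the pregnancy begins, not when it must be found. Day 7 and D30 fall inside the window. D180 and D365 fall after it, but could still bring to light a pregnancy that began within it. All four belong to the same 600, so counting the later visits does not change the 1%.

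**4. Other contacts**

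- Vaccinees outside the subset are encouraged to come to the adverse event monitoring cell, which runs for the vaccination period plus 7 days.
- Under Surveillance for enteric fever, staff visit all listed households periodically. No interval is given, and the stated purpose is to remind families to seek care for fever.
- Neither the day-7 information list nor the procedures listed for the three later subset visits includes a question on pregnancy.

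**The case against.** The strongest reply is that the sections do not contradict each other outright. One sets who may be vaccinated, one gives advice and one sets who receives outcome visits, and staff can obey all three. A broad precaution at entry with a narrower follow-up group can be a deliberate choice, and the protocol commits itself to respect for local culture and social values. This stands in part: the conflict is one of scope, and asking every unmarried girl about pregnancy is a debatable trade-off. It does not explain why a pregnancy already known to staff should have no outcome follow-up.

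A second reply is that routine follow-up may include the household visits, and that form items can be left to operating procedures. That is possible, and the word *all* in the section fits it better than a 600-child limit does. The text does not say so, however, and describes those visits by another purpose.

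Three stronger readings are tempting but not supported:

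- **Unmarried girls get the weaker entry check.** The documents do not compare the sensitivity of a urine test with that of deferral by menstrual date. By number of girls deferred, the rule for unmarried girls may be the stricter one.
- **Nothing would be recorded for an unmarried girl.** Serious adverse events are recorded for all participants throughout the study, and congenital anomaly counts as serious. The closing sentence of Pregnancy follow-up carries no marital limit of its own. What she lacks is scheduled follow-up to outcome.
- **A large number of exposed pregnancies is missed.** The documents give no marriage or pregnancy rate at these ages. Scaling up by assumed ages and sex ratio would count girls, not exposed pregnancies.

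**Conclusion.** The point holds as a mismatch of scope in safety follow-up. As written, an exposed pregnancy known in an unmarried girl has no scheduled outcome follow-up, although the entry rules and the advice reach her. This rests on reading the menstrual-date rule as a pregnancy precaution. The three-month advice supports the point independently, because it has no marital limit.

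The identification route is a lesser but real weakness. Dated individual contacts cover 1% of planned vaccinees, at most 200 of them in the relevant age stratum, and the protocol does not say whether the household visits count as routine follow-up.

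The number of exposed pregnancies affected is unknown and could be very small. The effectiveness estimate, the sample size and the immunogenicity objective are not affected.

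**What to change.** Reconcile Pregnancy follow-up with the exclusion criteria and the Vaccination section:

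1. Remove the marital limit, so that any vaccinated girl known to have been pregnant at vaccination, or to have become pregnant within three months, is in outcome follow-up.
2. State that routine follow-up includes the periodic household visits described under Surveillance for enteric fever, and that pregnancies that come to light there are recorded confidentially.

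This concerns who is followed and recorded. It proposes no change to the vaccination rule and does not require every unmarried girl to be questioned.

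The cost is a change of wording in one section, a place to record the information at visits already planned, and possibly a few more pregnancies to follow. The downside is the need for private, culturally sensitive handling, above all for unmarried girls.
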